4. SUBJECT INFORMATION

4.1. Demographics and Baseline Characteristics

Unless specified otherwise, all demographic and baseline characteristics variables will be summarized for the all treated analysis set.

The distribution of subject enrollment will be presented according to region and country. Subjects who did not meet study inclusion/exclusion criteria will be listed by subject ID, and specific criteria not met.

Subject demographic and baseline characteristic variables: age (< 65 years, 65 to < 75 years, and ≥75 years), sex, ethnicity, race, weight (kg), height (cm), and ECOG performance status will be summarized. A listing of subject demographic and baseline characteristics will be provided as well.

Baseline disease diagnosis including CD38 expression, β 2-microglobulin, and months since initial diagnosis will be summarized. A listing of disease diagnosis will be provided as well.

Medical history collected at baseline or screening visit will be summarized by system-organ class and preferred term.

4.2. Disposition Information

An overview of subject disposition will be provided. The overview includes a summary of total number of subjects who are treated. For all treated subjects (defined as subjects who have received at least 1 administration of daratumumab), the number and percentage of subjects who discontinued study treatment including reason for discontinuation as indicated by the investigators will be summarized. The similar summaries will be presented for all treated subjects who discontinued from study participation.

A listing of subjects who discontinued study treatment or study participation including reasons for discontinuation will be provided.

4.3. Treatment Compliance

Compliance will be analyzed as part of exposure. Please refer to 4.4

4.4. Extent of Exposure

Extent of exposure to study treatment will be summarized and presented based on all treated population.

The number and percentage of subjects treated within each cycle will be summarized. The maximum number of treatment cycles received for each subject will be summarized by frequency and descriptive statistics.

Duration of study treatment, defined as the number of days from the date of the first administration of study treatment to the date of the last administration of study treatment, will be summarized. The number of daratumumab infusions will be summarized for all treated subjects.

Daratumumab dose intensity, which is defined as the sum of total dose administered (mg/kg) in all cycles divided by the number of treatment cycles, will be summarized. Additionally, the daratumumab dose intensity will be summarized for cycles with high-intensity (Cycles 1-2) or low-intensity (Cycles 3-6 and Cycles 7+).

The relative dose intensity (%) defined as the ratio of total actually received dose and total planned dose will be calculated and summarized using descriptive statistics.

The number of subjects with cycle delays or dose modifications (dose delays or dose skipping) including reasons (AE or other) for cycle delays or dose modifications, will be reported.

A listing of subjects with daratumumab infusions will be provided.

4.5. Protocol Deviations

A listing of subjects with major protocol deviations including subject ID, type of deviation, and reasons for deviation will be provided.

4.6. Prior Medications

A summary of prior therapies (systemic therapy, radiotherapy, or cancer-related surgery/procedure) will be provided. Specifically, the number of prior lines of therapy will be calculated and summarized by the following categories: 1, 2, or ≥ 3 through frequency and descriptive statistics. Additionally, the prior systemic therapy will be summarized by therapeutic class, pharmacologic class and drug name.

4.7. Concomitant Medications

Concomitant medications collected in the CRF page during the study will be summarized by therapeutic class, pharmacologic class, and drug name. A similar summary will be provided for pre-infusion medication and post-infusion medication, respectively. A listing will be provided for pre-infusion medication and post-infusion medication, respectively.

4.8. Subsequent Anticancer Therapy

The total number of subjects who received subsequent anticancer therapy will be reported. A summary of subsequent anticancer therapy will be presented by therapeutic class, pharmacologic class and drug name.

5. EFFICACY

5.1. Analysis Specifications

The analysis of efficacy will be based on BICR for all treated population. Sensitivity analysis will be performed based on investigators' assessment.

5.1.1. Level of Significance

Not applicable.

5.1.2. Data Handling Rules

No data imputation will be performed for missing efficacy endpoint values.

5.2. Primary Efficacy Endpoint(s)

Study will evaluate evidence of clinical responses with primary efficacy endpoint of objective response rate.

5.2.1. Definition

Objective response rate (ORR) is defined as the proportion of subjects who achieve CR or PR per Revised Criteria for Response Assessment of Hodgkin and non-Hodgkin lymphoma: LUGANO classification based on BICR.

5.2.2. Analysis Methods

An estimate of the ORR will be presented along with a two-sided 95% exact confidence interval. The number and percentage of subjects in the following response categories will be presented: complete response (CR), partial response (PR), stable disease (SD), progressive disease (PD), not evaluable (NE), overall response (CR+PR) and Clinical benefit rate (CR+PR+SD).

5.3. Secondary Endpoints

Secondary endpoints include complete response (CR) rate, progression-free survival (PFS), duration of objective response (DOR), time to response, and overall survival (OS).

5.3.1. Definition

Complete response (CR) rate is defined as the proportion of subjects who achieve CR based on BICR and will be analyzed similarly as the primary endpoint ORR.

Progression-free survival (PFS) is defined as the duration from the date of the first daratumumab dose to the date of progression/relapse based on BICR or death, whichever comes first. For those subjects who are still alive without progression/relapse, PFS will be censored at the last adequate tumor assessment. Subjects who are progression-free and alive or have unknown status will be censored at last tumor assessment. Subjects with no post baseline disease assessment will be censored on Day 1. Subjects who started a subsequent anti-cancer therapy in the absence of progression will be censored at the last disease assessment before the start of subsequent therapy. Subjects whose diseases have not progressed and who are still alive at the end of the study or clinical cutoff will be censored at the last adequate disease assessment.

Duration of response (DoR) will be duration from the date of the initial documentation of a response to the date of first documented evidence of progressive disease based on BICR (PD; or relapse for subjects who experience CR) or death and calculated only for responders. For those subjects who are still without progression/relapse, DoR will be censored at the last adequate tumor assessment.

Time to response (TTR) is defined as the duration from the date of the first dose of daratumumab to the earliest date that a response (CR/PR based on BICR) is first documented. Descriptive analysis will be performed for responders including median, mean, standard deviation, and range.

Overall survival (OS) is defined as the duration from the date of the first daratumumab dose to the date of death. Subjects who withdraw consent from the study or are lost to follow-up will be censored at the time of withdrawal or lost to follow-up. For those subjects who are still alive at the time of analysis, OS will be censored at the last date known to be alive.

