Inclusion/exclusion criteria ^a	X									
Medical history and demographics	X									
FEV1 for subjects with COPD	X									
Tumor sample ^c	X									
ECOG ^f	X	X				X		X	X	8 wks post PD
Pregnancy test (serum/urine) ^b	X	As clinically indicated							X	
Study Drug Administration										
Daratumumab ^h		X	X	X	X	X	X	X		
Safety Assessments										
Physical examination (including neurological examination, lymphoma B-symptoms will be recorded separately)	X	Symptom and disease directed exam as clinically indicated								
Weight ^e	X	X				X		X		
Height	X									
Vital signs ^g	X	X	X	X	X	X	X	X		
12-lead ECG	X					C3D1, C6D1			X	
Lymphoma B-symptoms ^o	X	X				X		X	X	
Clinical Laboratory Assessments										
Hematology ^d	X	X	X	X	X	X	X	X	X	
Clinical chemistry ^d	X	X				X		X	X	
Hepatitis B ^p and C serology (local laboratory)	X									
HBV DNA testing ^q	X	Every 12 weeks upto 6 months after last dose of daratumumab								
ABO, Rh and IAT		X (predose)								
β ₂ -microglobulin (central laboratory)	X									
Pharmacokinetics/ Immunogenicity										

TIME AND EVENTS SCHEDULE

Phase	Screening	Treatment						EoT	FU ^k
		Day 1 of each cycle (4-week cycles)							
Period	Within 21 days of Cycle 1 Day 1	Cycle 1 and 2			Cycle 3 to 6		Cycle 7+	Within 30 days of last dose	Q8 weeks
Day	-21 to -1	D1	D8	D15	D22	D1	D15	D1	±2 weeks
Study Procedures									
Daratumumab PK and Immunogenicity	Please see T&E Schedule: PK and Immunogenicity In addition, any time an IRR is observed during the study, an unscheduled blood sample should be drawn as soon as possible after the reaction for potential immune response analysis ^l								
Disease Evaluations: Refer to Section 8.2 for details.									
PET-CT scan	X ⁿ	Every 8 weeks (±7 days) for the first 6 months; thereafter, every 16 weeks (±7 days)							
CT or MRI imaging (neck, chest, abdomen, and pelvis) ⁱ	X ⁿ	Every 8 weeks (±7 days) for the first 6 months; thereafter, every 16 weeks (±7 days)							
Circulating plasma EBV-DNA quantification (central laboratory)		X				X		X	
Bone marrow biopsy	X (optional)	Required to confirm CR, regardless of whether biopsy was performed at screening							
Tumor biopsy (optional)	X ^m	As clinically indicated ^m							
Subsequent therapy									X
Other new malignancy									X
Survival									X
Biomarkers									
Whole blood collection ^j		C1D1 (predose)			C3D1 (predose)	C7D1 (predose)		X	
Ongoing Subject Review									

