4.1. Inclusion Criteria

Each potential subject must satisfy all of the following criteria to be enrolled in the study:

1. At least 18 years of age
2. Documented as histologically confirmed extranodal NK/T-cell lymphoma, nasal type according to the World Health Organization (WHO) classification,^{10,13,20} and the pathology report will be verified by the Sponsor.
3. Criterion modified per Amendment 1:
 - 3.1 Failed (relapsed or refractory after achieving complete or partial remission) at least 1 line of chemotherapy, and who, according to treating physician or investigator, is not candidate to receive other treatment modalities.
4. Criterion modified per Amendment 1:
 - 4.1 At least 1 measurable site of disease (see Section 8.2.1), which should be positive ¹⁸F-fluorodeoxyglucose (FDG) uptake in nodal or extranodal sites on positron emission tomography (PET) scan.
5. ECOG performance status score of 0, 1 or 2. (refer Attachment 1) and life expectancy ≥ 3 months.
6. Subject must have pretreatment clinical laboratory values meeting the following criteria during the Screening Phase:
 - a. hemoglobin ≥ 7.5 g/dL (≥ 4.65 mmol/L) without transfusion support within 7 days;
 - b. absolute neutrophil count (ANC) $\geq 0.75 \times 10^9/L$ (ie, $\geq 750/\mu L$) without growth factor support within 7 days;
 - c. platelet count $\geq 50 \times 10^9/L$ without transfusion support within 7 days;
 - d. aspartate aminotransferase (AST) ≤ 2.5 x upper limit of normal (ULN);
 - e. alanine aminotransferase (ALT) ≤ 2.5 x ULN;
 - f. total bilirubin ≤ 1.5 x ULN, except in subjects with congenital bilirubinemia, such as Gilbert syndrome (in which case direct bilirubin ≤ 1.5 x ULN required);
 - g. calculated creatinine clearance of ≥ 30 mL/min (refer Attachment 5: Calculation of Creatinine Clearance using Cockcroft-Gault formula);
7. Criterion modified per Amendment 1:
 - 7.1 Women of childbearing potential must commit to either abstain continuously from heterosexual sexual intercourse or to use 2 methods of reliable birth control simultaneously. This includes one highly effective form of contraception (tubal

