8.2.6. Blinded Independent Central Review

An independent review of all scans and clinical information used in the assessment of tumors will be conducted according to the Revised Criteria for Response Assessment: LUGANO classification.¹² All imaging assessments including unscheduled visit scans will be collected on an ongoing basis and sent to a sponsor appointed CRO for central analysis. The central review process will be clearly defined in a BICR charter in advance of the start of the study.

The treatment discontinuation due to PD will be based upon the results of the real time central review. This procedure may not be followed if the clinical information of subject (eg, Pathologically demonstrated PD) is sufficient enough to demonstrate PD, for such cases, PD confirmation from sponsor study physician is also required.

The efficacy analysis for this study will be based on the BICR data.

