10.3.2. Secondary Efficacy Endpoint

Complete response (CR) rate is defined as the proportion of subjects who achieve CR based on BICR and will be analyzed similarly as the primary efficacy endpoint.

Progression-free survival (PFS) is defined as the duration from the date of the first daratumumab dose to the date of progression/relapse based on BICR or death, whichever comes first. For those subjects who are still alive without progression/relapse, PFS will be censored at the last adequate tumor assessment.

Duration of response (DoR) will be duration from the date of the initial documentation of a response to the date of first documented evidence of PD based on BICR (PD; or relapse for subjects who experience CR) or death. For those subjects who are still without progression/relapse, DoR will be censored at the last adequate tumor assessment.

Time to response is defined as the duration from the date of the first dose of daratumumab to the earliest date that a response (CR/PR based on BICR) is first documented. For nonresponders, it will be censored at the date of PD/relapse or the date of the last adequate disease assessment, whichever comes first.

Overall survival (OS) is defined as the duration from the date of the first daratumumab dose to the date of death. For those subjects who are still alive without progression/relapse, OS will be censored at the last date known to be alive.

For time to event endpoints (eg, PFS, OS, time to response, DoR), Kaplan-Meier estimates will be presented. Median along with corresponding 95% CIs will be obtained from the Kaplan-Meier estimates. Analysis for time to response and DoR will be for responders only.

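### The SAP's Day-1 censoring rule for PFS does not exempt deaths, so an early death without a scan is both an event and a Day-1 censoring

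*SAP*

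**What the plan says.** SAP 5.3.1 measures PFS from the first daratumumab dose "to the date of progression/relapse based on BICR or death, whichever comes first". Five censoring sentences follow, and they are not worded alike.

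- Three depend on vital status. The first is the sentence that the SAP shares with Protocol 10.3.2: "For those subjects who are still alive without progression/relapse, PFS will be censored at the last adequate tumor assessment". The second is "Subjects who are progression-free and alive or have unknown status will be censored at last tumor assessment". The third covers subjects alive and progression-free at study end or clinical cutoff.
- Two do not. One is the Day-1 rule: "Subjects with no post baseline disease assessment will be censored on Day 1". The other is the subsequent-therapy rule: "Subjects who started a subsequent anti-cancer therapy in the absence of progression will be censored at the last disease assessment" before that therapy.

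Protocol 10.3.2 has the same event definition, censors only living subjects, and has no Day-1 rule. PFS is analysed in all treated subjects (SAP 2.8.1 and 5.1), so no post-baseline scan is needed to be included. Disease evaluations are every 8 weeks for the first 6 months (Protocol 3.1 and 8.2). SAP 2.1 computes durations as the date difference plus 1 day.

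**The concern.** A treated subject who dies before any post-baseline assessment meets two statements in the same paragraph: the event definition and the Day-1 rule. Neither document says which prevails. The phrase about whichever comes first orders progression against death; it does not order death against censoring. Two programmers could follow the same text and produce different PFS curves.

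The literal reading errs in one direction. It removes the earliest deaths, which belong to the subjects who did worst, and so raises the curve. This is a single-arm trial, so no comparator carries the same bias. The investigator-assessed sensitivity analysis in SAP 5.1 has no separate rule and inherits the ambiguity.

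**Working it through.** **Plan's own figures.** The documents state no PFS assumption to reproduce. The one fully specified design is the Simon rule in SAP 1.4: continue with at least 2 of 15 responses, reject with at least 8 of 32. The rejection probability is the sum over x ≥ 2 of P(X₁₅ = x) × P(X₁₇ ≥ 8 − x). It is 0.781 at an ORR of 30% and 0.094 at 15%, in line with the stated 78% power and 10% one-sided alpha. PFS does not enter this calculation.

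**One subject.** Take a death on study day 30 with no scan.
- By the event definition: event at 29 + 1 = 30 days.
- By the literal Day-1 rule: censored at 0 + 1 = 1 day, and absent from every later risk set.

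**The curve.** Let d of N treated subjects die before any assessment, and let q = d/N. Assume no other censoring before the last of these deaths. If m subjects are still event-free after that death, the two estimates are:
- deaths as events: m/N;
- deaths censored on Day 1: m/(N − d).

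The ratio is N/(N − d) = 1/(1 − q). It persists, because the two risk sets are identical from then on.

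| d of 32 | PFS just before week 8, deaths as events (no other events) | Same, Day-1 censoring | Factor on later PFS |
|---|---|---|---|
| 2 | 30/32 = 93.8% | 100% | 1.07 |
| 3 | 29/32 = 90.6% | 100% | 1.10 |
| 5 | 27/32 = 84.4% | 100% | 1.19 |

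For an assumed q of 5%, 10% or 15% the factor is 1/0.95 = 1.05, 1/0.90 = 1.11 or 1/0.85 = 1.18. An assumed true 6-month PFS of 30% would then be reported as 31.6%, 33.3% or 35.3%.

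**How large might q be?** The documents do not say. Protocol section 1 offers two survival figures, neither for this population: a median OS of about 8 months in all NKTCL patients, and 55% one-year OS in a phase 2 study of combination chemotherapy. Under an assumed exponential curve, the share dead by day 56 is:
- 8-month median (243.5 days): 1 − 0.5^(56/243.5) = 14.7%, or 4.7 of 32;
- 55% at one year: 1 − 0.55^(56/365.25) = 8.8%, or 2.8 of 32.

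Not every such death is unscanned. If half follow an unscheduled scan (an assumption), q is 7.4% or 4.4%, and the factor is 1.08 or 1.05.

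These are illustrations, not bounds. Entry criterion 5 requires an ECOG score of 0 to 2 "and life expectancy ≥ 3 months", and Protocol 8.2.6 says "All imaging assessments including unscheduled visit scans will be collected on an ongoing basis"; both push q down. In the other direction, an exponential with an 8-month median implies a 5-year OS of 0.5^(60/8) = 0.6%, whereas the Protocol reports 32% for the same patients. That mismatch suggests a higher early hazard than the exponential assumes.

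**The median.** The inflated curve crosses 50% where the correct curve is at 50% × (1 − q), for example 45% when q = 10%. Progression is mostly read at scans 8 weeks apart, so the curve falls in steps. The median may therefore move by days or not at all.

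**The case against.** The paragraph has a sensible ordinary reading. It defines the event first and then lists censoring rules, and censoring normally concerns subjects who have had no event. The Day-1 sentence directly follows the one for subjects alive or of unknown status, and it supplies the case that sentence leaves open: no assessment to censor at. On that reading nothing conflicts. Protocol section 10 leaves detail to the SAP, so adding a Day-1 rule is elaboration and not in itself a departure.

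The consequence is also limited. PFS is secondary and descriptive. SAP 5.3.2 reports numbers of events and censored subjects, SAP 6.2.1 lists deaths, and OS is analysed separately. With 32 subjects and a PFS of 30%, the sampling margin is about 1.96 × √(0.3 × 0.7/32) = 16 percentage points, well above the 1.6 to 5.3 points illustrated.

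Most of this stands, and it sets the grade. What it does not supply is the missing words: the precedence has to be assumed by the reader, and the bias on the literal reading is systematic where sampling error is not.

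A reader might infer that the SAP has decided to exclude early deaths from PFS, or that it flatly contradicts the protocol. The documents do not support this. The same paragraph names death as an event, and the departure from Protocol 10.3.2 exists only on the literal reading.

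**Conclusion.** The point holds as a drafting ambiguity that can produce a wrong result. The Day-1 sentence lacks a no-event condition and no rule of precedence is stated. If it is applied literally, Kaplan-Meier PFS after the early deaths is too high by a factor of 1/(1-q), or 1.05 to 1.18 for an assumed q of 5% to 15%. That size depends on a programmer taking the literal reading and on a share q that the documents do not give. The background survival figures neither fix q nor bound it, so it should not be said that PFS will be inflated by a particular amount.

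Nor does the problem extend to other endpoints. ORR and the Simon rule use response counts, OS has its own censoring rules, and responders in the DoR analysis have a post-baseline assessment by definition. Severity: minor.

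**What to change.** Replace the Day-1 sentence in SAP 5.3.1 with wording such as:

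*A subject who has no PFS event (alive or of unknown status) and no post-baseline disease assessment is censored on Day 1. A death before the first post-baseline assessment is a PFS event on the date of death.*

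Add one sentence for the subject who starts new anti-cancer therapy before any post-baseline assessment. It should say whether the existing subsequent-therapy censoring takes precedence over a later death, and at what date the subject is then censored, because the only earlier assessment is the one at screening. Apply the same rules to the BICR and the investigator-assessed analyses.

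The cost is one or two sentences before PFS is programmed. No new data are needed, since death and subsequent therapy are already recorded in follow-up. The one downside is that reported PFS may be slightly less favourable than under the literal rule.

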For subjects who have PD as evidenced by unambiguous clinical information (eg. pathologically demonstrated as PD) without confirmation by BICR, they may be discontinued from study treatment at the investigator's discretion. Before such subjects discontinue study treatment, sites will document PD by completing and faxing a PD form to the sponsor as soon as possible and within 48 hours of PD assessment. The study responsible physician will provide written confirmation that treatment should be discontinued. After written confirmation from the sponsor, study treatment may be discontinued and recorded in IWRS before the subject can enter the Follow-up Phase.

Subjects should be discontinued from study treatment if they have objective radiological PD by BICR, however, subjects may be allowed to continue study treatment if PD was documented only by local evaluation and the investigator believes, and sponsor study physician concurs, that the subject could continue to receive benefit and will not experience serious toxicity, and there is no available better alternative treatment that could benefit the subject. These subjects will continue study procedure as per [T&E Schedule](#). If subsequent PD is confirmed either by centrally diagnosis or clinical judgement per investigator discretion, the subject must be discontinued from the study treatment, a subsequent PD form is required for study physician to provide the written confirmation for subject discontinued the study treatment.

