8.1.4. Posttreatment Phase (Follow-Up)

The Follow-up Phase will begin once a subject discontinues study treatment, the date of discontinuation of study treatment is based on the study physician's written confirmation date in the PD form. Subjects who discontinue before PD (for other reasons such as an AE) must continue to have their regularly scheduled scans according to the [T&E Schedule](#) until centrally confirmed PD, death, the start of a new anticancer therapy, withdrawal of consent, lost to follow-up, or the end of the study. After PD is centrally evidenced with study physician's confirmation of PD form, follow-up will occur at least every 8 weeks (± 2 weeks). Subsequent anticancer therapy, second primary malignancies, and survival status will be recorded.

If the follow-up information is obtained via telephone contact, written documentation of the communication must be available for review in the source documents. If the subject has died, the date and cause of death will be collected and documented in the eCRF.

Investigators may recontact the subject to obtain long-term follow-up information regarding the subject's safety or survival status as noted in the informed consent form (refer to Section [15.2.3](#), Informed Consent).

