For subjects who have PD as evidenced by unambiguous clinical information (eg. pathologically demonstrated as PD), before such subjects discontinue study treatment due to PD, sites will document PD by completing and faxing a PD form to the sponsor as soon as possible and within 48 hours of PD assessment; EoT steps will be performed. The study responsible physician will confirm that treatment should be discontinued. After confirmation from the sponsor, study treatment may be discontinued and the subject can enter into Follow-up phase. If a subject discontinues study treatment for any reason other than PD, then disease assessments should be obtained as specified in the [T&E Schedule](#).

Withdrawal From the Study

A subject will be withdrawn from the study for any of the following reasons:

- Lost to follow-up
- Withdrawal of consent
- Death
- Sponsor terminates the study.

If a subject is considered lost to follow-up, every reasonable effort must be made by the study-site personnel to contact the subject and determine the reason for discontinuation/withdrawal. The measures taken to follow up must be documented.

When a subject withdraws before completing the study, the reason for withdrawal is to be documented in the eCRF and in the source document (refer Section [8.1.4](#) and Section [15.2.3](#) for details on collection of long-term survival status). Study drug assigned to the withdrawn subject

may not be assigned to another subject. Subjects who withdraw will not be replaced. If a subject withdraws from the study before the EoT, assessments should be obtained.

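### Progression accepted by the sponsor without BICR confirmation is not a PFS or DoR event, and a therapy switch then censors PFS before that progression

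*SAP*

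**What the plan says.** **Stopping.** Treatment normally stops on progression read by the real-time central review. Protocol 8.1.3 adds a second route for "PD as evidenced by unambiguous clinical information (eg. pathologically demonstrated as PD) without confirmation by BICR". The site completes a PD form and the study responsible physician confirms in writing. Protocol 8.2, 8.2.6 and 9.2 carry the same exception.

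**Endpoints.** In SAP 5.3.1 (and protocol 10.3.2) PFS runs to "the date of progression/relapse based on BICR or death, whichever comes first". DoR runs to "the date of first documented evidence of progressive disease based on BICR (PD; or relapse for subjects who experience CR) or death".

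**Censoring.** For PFS: "Subjects who started a subsequent anti-cancer therapy in the absence of progression will be censored at the last disease assessment" before that therapy. A subject with no post-baseline assessment is censored on Day 1. For DoR the only rule is: "For those subjects who are still without progression/relapse, DoR will be censored at the last adequate tumor assessment".

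**Scans after stopping.** Protocol 8.1.4: "Subjects who discontinue before PD (for other reasons such as an AE) must continue to have their regularly scheduled scans", and these run to centrally confirmed PD, new therapy or another listed end. Protocol 9.2: "If a subject discontinues study treatment for any reason other than PD, then disease assessments should be obtained". Time and Events footnote k adds scheduled scans only for those who stop for reasons other than PD.

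**Related text.** BICR receives clinical information as well as images (protocol 8.2, 8.2.6) and site biopsy pathology (8.2.5). SAP 5.1 plans a sensitivity analysis on investigators' assessment.

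**The concern.** The stopping rule recognises a progression that the endpoint rule does not. A subject with biopsy-proven progression, accepted by the sponsor, can leave treatment with no BICR event. If that subject then starts other therapy, PFS is censored at a scan that predates the progression. The reason for the censoring is the progression itself, so the Kaplan-Meier assumption of non-informative censoring fails, and in a known direction. There is no control arm in which the same error could partly cancel.

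For DoR the sponsor-confirmed progression is likewise not an event.

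The follow-up wording decides how often a later scan could rescue the event, and it does not place these subjects. Footnote k and 9.2 turn on whether the reason for stopping was PD. Section 8.1.4 speaks of stopping before PD but ends the scans at centrally confirmed PD. A subject with PD that is not centrally confirmed fits neither group cleanly.

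**Working it through.** **The plan's own figures.** The documents give no PFS or DoR target and no rate of clinical-only progression, so there is no PFS figure to reproduce. The ORR design does reproduce. Continuing with at least 2 of 15 and rejecting with at least 8 of 32, the sum over x = 2 to 15 of P(X1 = x) × P(X2 ≥ 8 − x), with 15 and 17 subjects, is 0.781 at ORR 30% (stated 78%) and 0.094 at 15% (limit 10%). PFS does not enter it.

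**Inputs for PFS**
- From the documents: scans every 8 weeks for 6 months, then every 16 weeks, taken as weeks 8, 16, 24, 40.
- Assumed: exponential time to progression with median 13 weeks; share f of progressions that are clinical-only and never adopted by BICR, 10%, 20% or 30%; all of these subjects switch therapy and are censored at the previous scan (Day 1 if none); all other progressions are dated at the next scan.

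**Planned rule.** Survival over one 8-week interval is q = 2^(−8/13) = 0.6528. Clinical-only progressors in an interval leave the risk set before the scan that ends it. Each Kaplan-Meier factor is therefore q / [1 − f(1 − q)] instead of q, and the estimate at week 26 (after three scans) is its cube.

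**Comparator.** Clinical PD is an event on its own date. At week 26 the estimate is S(24) − f[S(24) − S(26)], with S(24) = 0.2781 and S(26) = 0.25.

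| f | Factor | Planned, week 26 | Comparator, week 26 | Excess (points) |
|---|---|---|---|---|
| 10% | 0.6528 / 0.9653 = 0.676 | 0.309 | 0.275 | 3.4 |
| 20% | 0.6528 / 0.9306 = 0.701 | 0.345 | 0.273 | 7.3 |
| 30% | 0.6528 / 0.8958 = 0.729 | 0.387 | 0.270 | 11.7 |

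**Median.** The planned curve at week 16 is the factor squared: 0.457, 0.492 and 0.531. The median is therefore week 16 at f = 10% and 20%, and week 24 at 30%. The comparator stays above 0.5 until just before week 16 (0.585 at f = 30%) and falls to 0.426 there, so its median is week 16 throughout.

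**Longer true median.** At 26 weeks, q = 0.8079 and the same formulas give 0.559 vs 0.525, 0.593 vs 0.522 and 0.630 vs 0.519, an excess of 3.4, 7.1 and 11.1 points.

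**Not everyone switches.** A simulation of 20,000 subjects per scenario used a true median of 4 months, f = 30% and cutoffs 9 to 18 months after first dose. It gave 6-month PFS of 50% against 38% if all switch. With half switching and the rest dying a mean of 3 months later, it gave 46% against 37%. The bias shrinks but stays upward, because a death counted in place of an earlier progression is still a late event.

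**The case against.** **BICR is not limited to images.** It reviews clinical information and site pathology, and Attachment 6 includes marrow involvement and unequivocal assessable disease. The phrase about lacking BICR confirmation governs when treatment may stop; it does not say BICR will never adopt the progression. This stands: only unadopted cases are lost, and their share could be near zero. But no text makes sponsor-confirmed PD a BICR event or fixes its date.

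**Scans may continue.** A reader might infer that scanning stops for these subjects. Section 8.1.4 can equally be read as continuing scans to centrally confirmed PD. The documents support only that the three places do not agree. Even on the longer reading, scans end at new therapy, so a prompt switch still loses the event.

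**DoR.** A reader might infer that DoR is also censored at a switch. The subsequent-therapy rule is written for PFS only, and a death after a switch remains a DoR event.

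**The median.** A reader might scale it by 1/(1 − f), that is 1.11, 1.25 or 1.43. That needs progression dated continuously; with BICR progression dated at scans, the median often does not move. SAP 5.3.2 lists medians and plots, not a 26-week rate, so the excess above would be seen on the curve.

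**Few may switch.** Inclusion criterion 3.1 takes subjects who are not candidates for other modalities. This reduces the bias, but subsequent therapy is still collected and summarised.

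**A sensitivity analysis exists.** SAP 5.1 partly covers the gap. It does not say whether clinical PD counts there or on what date, and it changes the assessor for every subject.

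**Conclusion.** The point holds in a limited form. Read together, the stopping, endpoint and censoring rules can censor PFS before a progression the sponsor has confirmed, and the bias was upward in every scenario examined. For DoR the same progression is not an event, although a later death is. With a 13-week true median, scan-dated BICR progression and all affected subjects switching, the excess in 26-week PFS is about 3, 7 or 12 points at shares of 10%, 20% or 30%; the median is unchanged at 10% and 20% and moves from 16 to 24 weeks at 30%. The shares are assumptions, and if BICR adopts nearly all such cases the effect vanishes.

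The documents do not support reading this as a threat to the trial's main conclusion. ORR, its alpha and its power are untouched, and PFS and DoR are descriptive secondary endpoints. This is a cheap improvement.

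**What to change.** 1. Keep the BICR versions of PFS and DoR as the main analysis. Replacing them would bring a non-independent judgement into a BICR endpoint of an open-label trial. Add to SAP 5.3.1 a prespecified supplementary analysis of both, in which PD confirmed in writing by the sponsor physician through the PD-form route is an event at its PD date when no earlier BICR PD exists. Report how many subjects this concerns.
2. Reconcile protocol 8.1.4, 9.2 and Time and Events footnote k, so that they state the same scan follow-up for subjects who stop without BICR-confirmed PD.

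Cost: one extra analysis from a form already collected, a short protocol clarification, some further scheduled scans if the reconciled text continues them, and slightly less favourable supplementary estimates.
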